7.7.2 Analysis

No statistical tests will be performed.

7.7.3 Presentation

All organ failure variables will only be presented in listings together with the definition variables.

7.8 Secondary Endpoints – SOFA score

7.8.1 Definition

The total SOFA score will be calculated using all including parts:

Respiration Score, Coagulation Score, Liver Score, Cardiovascular Score, Central Nervous System Score, Renal Score in accordance to:

Table 1. Sequential [Sepsis-Related] Organ Failure Assessment Score^a

System	Score				
	0	1	2	3	4
Respiration					
PaO ₂ /Fio ₂ , mm Hg (kPa)	≥400 (53.3)	<400 (53.3)	<300 (40)	<200 (26.7) with respiratory support	<100 (13.3) with respiratory support
Coagulation					
Platelets, ×10 ³ /μL	≥150	<150	<100	<50	<20
Liver					
Bilirubin, mg/dL (μmol/L)	<1.2 (20)	1.2-1.9 (20-32)	2.0-5.9 (33-101)	6.0-11.9 (102-204)	>12.0 (204)
Cardiovascular					
	MAP ≥70 mm Hg	MAP <70 mm Hg	Dopamine <5 or dobutamine (any dose) ^b	Dopamine 5.1-15 or epinephrine ≤0.1 or norepinephrine ≤0.1 ^b	Dopamine >15 or epinephrine >0.1 or norepinephrine >0.1 ^b
Central nervous system					
Glasgow Coma Scale score ^c	15	13-14	10-12	6-9	<6
Renal					
Creatinine, mg/dL (μmol/L)	<1.2 (110)	1.2-1.9 (110-170)	2.0-3.4 (171-299)	3.5-4.9 (300-440)	>5.0 (440)
Urine output, mL/d				<500	<200

Abbreviations: Fio₂, fraction of inspired oxygen; MAP, mean arterial pressure; PaO₂, partial pressure of oxygen.

^b Catecholamine doses are given as μg/kg/min for at least 1 hour.

^c Glasgow Coma Scale scores range from 3-15; higher score indicates better neurological function.

^a Adapted from Vincent et al.²⁷

The Modified Sequential Organ Failure Assessment (MSOFA) total score will be calculated excluding the Central Nervous System Score.

Absolute and percent changes for each including item and total score will be calculated.

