4.4 Definition of Baseline

Baseline measurement is defined as the latest measurement prior to first dose of IMP including Apache II score.

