4.5 Summary Statistics

In general, all data collected will be presented with summary statistics and given in patient data listings. Summary statistics will include at least number of patients, mean, standard deviation, median, minimum and maximum for continuous data and frequency and percentage for categorical data. Table with summary statistics will be divided by treatment group and dose group, and visit where applicable. Patient data listings will be sorted by treatment, subject and timing of assessments.

For confidence intervals for proportions will the Clopper-Pearson exact formula be used.

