4.8 Handling of Drop-outs, Missing Data and Outliers

Outliers will be included in summary tables and listings, and will not be handled separately in any analyses. No imputation of missing data will be performed (however, will data entered in unscheduled visit be placed to the nearest applicable visit with missing values).

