7 STATISTICAL METHODOLOGY

All parameters will be presented by treatment and visit using summary statistics. Additional statistical analyses are specified below.

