7.8.3 Presentation

All including item and total scores will be presented using summary statistics.

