7.11 Secondary Endpoints - Pain Numeric Rating Scale (PNRS)

7.11.1 Definition

The mean daily Pain Numeric Rating Scale (PNRS) score will be calculated using.

Pain Numeric Rating Scale

1. On a scale of 0 to 10, with 0 being no pain at all and 10 being the worst pain imaginable, how would you rate your pain RIGHT NOW.

0	1	2	3	4	5	6	7	8	9	10
No Pain										Worst Pain Imaginable

The absolute and percent change from baseline will be calculated.

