7.12 Secondary Endpoints - Critical-Care Pain Observation Tool (CPOT)

7.12.1 Definition

Critical-Care Pain Observation Tool (CPOT) total score will be calculated from each individual item along with absolute and percent change.

Indicator	Score	Description
Facial expression 
[name], B.Sc., PhD(student) School of Nursing, McGill University
	Relaxed, neutral	0 No muscle tension observed
	Tense	1 Presence of frowning, brow lowering, orbit tightening and levator contraction or any other change (e.g. opening eyes or tearing during nociceptive procedures)
	Grimacing	2 All previous facial movements plus eyelid tightly closed (the patient may present with mouth open or biting the endotracheal tube)
Body movements	Absence of movements or normal position	0 Does not move at all (doesn't necessarily mean absence of pain) or normal position (movements not aimed toward the pain site or not made for the purpose of protection)
	Protection	1 Slow, cautious movements, touching or rubbing the pain site, seeking attention through movements
	Restlessness/Agitation	2 Pulling tube, attempting to sit up, moving limbs/thrashing, not following commands, striking at staff, trying to climb out of bed
Compliance with the ventilator (intubated patients) OR Vocalization (extubated patients)	Tolerating ventilator or movement	0 Alarms not activated, easy ventilation
	Coughing but tolerating	1 Coughing, alarms may be activated but stop spontaneously
	Fighting ventilator	2 Asynchrony: blocking ventilation, alarms frequently activated
	Talking in normal tone or no sound	0 Talking in normal tone or no sound
	Sighing, moaning	1 Sighing, moaning
	Crying out, sobbing	2 Crying out, sobbing
Muscle tension Evaluation by passive flexion and extension of upper limbs when patient is at rest or evaluation when patient is being turned	Relaxed	0 No resistance to passive movements
	Tense, rigid	1 Resistance to passive movements
	Very tense or rigid	2 Strong resistance to passive movements or incapacity to complete them
TOTAL		___ / 8

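### Percent change on SOFA, PNRS and CPOT is undefined when the baseline score is 0, so patients who worsen from 0, or stay there, fall out of that summary and it can mislead in either direction

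*SAP*

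**What the plan says.** Three SAP sections derive a percent change on a score with a true zero.

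- **SOFA, 7.8.1** (six items scored 0-4, and the total): "Absolute and percent changes for each including item and total score will be calculated".
- **PNRS, 7.11.1** (0-10): "The absolute and percent change from baseline will be calculated".
- **CPOT, 7.12.1** (0-8): the "total score will be calculated from each individual item along with absolute and percent change".

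The denominator comes from SAP 4.4: "Baseline measurement is defined as the latest measurement prior to first dose of IMP including Apache II score". Sections 7.8.1 and 7.12.1 do not repeat that change is measured from baseline; I read them that way. Nothing in 4.4 or elsewhere says what to do when the baseline is 0, and SAP 4.8 states "No imputation of missing data will be performed".

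On presentation, SAP 4.5 says "Summary statistics will include at least number of patients, mean, standard deviation, median, minimum and maximum for continuous data", and the opening of SAP 7 adds "All parameters will be presented by treatment and visit using summary statistics". For SOFA, 7.8.3 says only "All including item and total scores will be presented using summary statistics"; it names neither percent change nor a graph. For PNRS and CPOT, 7.11.3 and 7.12.3 do call for graphs of percent change over time.

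**The concern.** A patient with baseline 0 has no percent change. Nobody at 0 can improve, so every patient lost this way either worsened or stayed normal. On a SOFA item, the patients who worsened are those with new organ dysfunction, which is the event a by-organ summary should keep. The percent-change summary can then disagree in sign with the absolute change in the same treatment group.

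Zero baselines are foreseeable. Under Protocol 4.1 a patient can enter on SIRS alone, and temperature, heart rate, respiratory rate or PaCO2, and white cell count are not SOFA components. Protocol 4.2 excludes a cardiovascular SOFA score of 4 at Screening and sets no lower bound on any item. CPOT is observed at rest (Protocol 8.11.13), where 0 is possible. PNRS zeros should be less usual, because abdominal pain is required for entry.

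Groups are small, so a few lost patients matter, and SAP 4.11 splits all secondary endpoints further by gender and HCT/ALB.

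**Working it through.** **Group sizes.** The cohorts are 4, 4, 8 and 8 (Protocol 3.1), and 4 + 4 + 8 + 8 = 24, which matches SAP 3.3. At 3:1 that gives 6 active and 2 control patients in the first phase, and 12 active and 4 control in the second. Controls total 6, or 3 per sex. The documents give no figure for percent change or for the share of patients with baseline 0, so everything below is constructed.

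**Formula.** Percent change = 100 × (follow-up − baseline) / baseline. At baseline 0 this is x/0 for a patient who worsens and 0/0 for one who stays; both are undefined.

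**Example 1: six patients, one SOFA item.**

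| Baseline | Follow-up | Absolute change | Percent change |
|---|---|---|---|
| 0 | 2 | +2 | undefined |
| 0 | 3 | +3 | undefined |
| 0 | 0 | 0 | undefined |
| 1 | 1 | 0 | 0 |
| 2 | 1 | −1 | −50 |
| 2 | 0 | −2 | −100 |

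Mean absolute change = (2 + 3 + 0 + 0 − 1 − 2)/6 = +0.33, which is worse. Mean percent change = (0 − 50 − 100)/3 = −50%, which is better, on n = 3.

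**Example 2: twelve patients, half at 0, no net change.** Six start at 0 (three go to 2, three stay) and six start at 2 (three go to 0, three stay). Mean absolute change = (3 × 2 − 3 × 2)/12 = 0, n = 12. Mean percent change = (3 × (−100) + 3 × 0)/6 = −50%, n = 6.

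**Example 3: twelve patients, one at 0, no net change.** One goes 0 to 1, one goes 1 to 0, five go 2 to 4 and five go 4 to 2. Mean absolute change = (1 − 1 + 10 − 10)/12 = 0. Mean percent change = (−100 + 5 × 100 − 5 × 50)/11 = 150/11 = +13.6%, n = 11. The sign reverses because a move of two points up from 2 counts +100%, while the same distance down from 4 counts −50%.

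**How the sign depends on the share at 0.** Take an assumed baseline distribution π and one-point moves with equal flow in both directions, 0.5 × min(π_i, π_j) between adjacent scores, so the true mean change is exactly 0. The mean percent change is then taken over baseline > 0.

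| Score | Assumed share at baseline 0 | Assumed π, from score 0 upward | Mean percent change |
|---|---|---|---|
| 0-4 item | 80% | .80, .10, .05, .03, .02 | −17.1% |
| 0-4 item | 50% | .50, .20, .15, .10, .05 | −10.4% |
| 0-4 item | 20% | .20 each | −3.1% |
| 0-4 item | 5% | .05, .35, .30, .20, .10 | +7.5% |
| Total, values 0-8 | 5% | .05, .20, .20, .18, .14, .10, .07, .04, .02 | +5.3% |

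First row worked through: the flows are .05, .025, .015 and .01. The sum is (.025 − .05)/1 + (.015 − .025)/2 + (.01 − .015)/3 − .01/4 = −.0342, and −.0342/.20 = −17.1%.

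**The case against.** The strongest reply is that little depends on this. The endpoints are secondary, no test is planned on any of them (SAP 7.8.2, 7.11.2, 7.12.2), and SAP 4.2 says the study is not powered for inference. The sentences that ask for percent change also ask for absolute change, which is defined at 0. Item and total scores are summarized, organ failure is listed with its defining variables (7.7.3), patient data are listed, and tables carry the number of patients (4.5), so a reduced n would be visible. One sentence restricting percent change to baseline > 0 would close the formal gap. All of this stands, and it sets the severity.

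Three stronger readings are tempting, and the documents do not support them.

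- A reader might infer that mean percent change always leans toward improvement. Worsening from a non-zero baseline stays in and is not capped at 100%, so the lean depends on how many patients start at 0. No baseline distribution is given.
- A reader might take −50% as the likely distortion. Examples 1 and 2 both start half the patients at 0 and were built to show the effect.
- A reader might say that new organ dysfunction disappears from the planned graphs. Percent-change graphs are specified only for PNRS and CPOT. For SOFA, even a percent-change table is inferred from SAP 4.5 and 7.

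What does not stand is that this is only a missing rule. With a baseline > 0 rule in place, percent change on these scores would still omit every worsening from 0 and could still contradict the absolute change.

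**Conclusion.** The concern holds as a minor point. Percent change is unsuitable for scores where 0 is a valid baseline. As written, the SAP loses every patient who worsens from 0 and every patient who stays there from that summary. The result can understate worsening, mainly for SOFA items where many start at 0; where few start at 0, as may be so for a total score, the asymmetry of percent change can push the mean the other way.

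Under the assumed models with no true change, the mean percent change ran from −17.1% to +7.5%. The small constructed groups gave −50% and +13.6%. These are illustrations under stated assumptions, not estimates for this trial. The case is strongest for SOFA items, plausible for CPOT and weakest for PNRS.

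**What to change.** In SAP 7.8, 7.11 and 7.12, delete percent change for SOFA items, SOFA and MSOFA totals, PNRS and CPOT, and remove it from the graphs in 7.11.3 and 7.12.3. Report the absolute change already planned. For SOFA items, add shift tables from baseline category to each visit, so that a move from 0 to a higher score is counted.

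If percent change is kept for any of these scores, restrict it to baseline > 0, show beside it the number excluded and their absolute changes, and state that it is not to be interpreted alone.

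The cost is small: a SAP edit, fewer percent-change outputs and some added shift tables. No new data are needed. Protocol 10.4 does not ask for percent change and leaves endpoint detail to the SAP, so no protocol text is contradicted.

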7.8.2 Analysis

No statistical tests will be performed.

7.8.3 Presentation

All including item and total scores will be presented using summary statistics.

7.9 Secondary Endpoints - Revised Atlantic Classification of Acute Pancreatitis

7.9.1 Definition

Revised Atlanta Classification of Acute Pancreatitis, is determined by transient or persistent organ failure (Section 7.7), and local or systemic complications (systemic complications is defined as exacerbation of pre-existing comorbidity).

Grades of Severity	
Mild	No organ failure No local or systemic complications
Moderately Severe	Organ failure that resolves within 48 hours and/or Local or systemic complications without organ failure
Severe	Persistent Organ Failure

7.9.2 Analysis

No statistical tests will be performed.

7.9.3 Presentation

The Revised Atlantic Classification of Acute Pancreatitis will be presented using frequency tables.

7.10 Secondary Endpoints - Determinant Based Classification of Acute Pancreatitis

7.10.1 Definition

Severity as defined by Determinant Based Classification of Acute Pancreatitis will be provided by CalciMedica in excel format in accordance to by subject:

	Mild AP	Moderate AP	Severe AP	Critical AP
(Peri)pancreatic necrosis	No	Sterile	Infected	Infected
	And	And/Or	Or	And
Organ Failure	No	Transient	Persistent	Persistent

The Excel file will have information regarding: Randomization number, outcome of (Peri)pancreatic necrosis. Organ failure will be captured in accordance with section 7.7.

7.10.2 Analysis

No statistical tests will be performed.

7.10.3 Presentation

The Determinant Based Classification of Acute Pancreatitis will be presented using frequency tables.

7.11 Secondary Endpoints - Pain Numeric Rating Scale (PNRS)

7.11.1 Definition

The mean daily Pain Numeric Rating Scale (PNRS) score will be calculated using.

Pain Numeric Rating Scale

1. On a scale of 0 to 10, with 0 being no pain at all and 10 being the worst pain imaginable, how would you rate your pain RIGHT NOW.

0	1	2	3	4	5	6	7	8	9	10
No Pain										Worst Pain Imaginable

The absolute and percent change from baseline will be calculated.

7.11.2 Analysis

No statistical tests will be performed.

7.11.3 Presentation

The PNRS will be presented using summary statistics with graphs over time presenting the mean, absolute and percent change.

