### **5.3 Prohibited Medications**

Any medication, with the exception of those listed below, may be given at the discretion of the PI. Immunosuppressive medications/immunotherapy that should not be administered during the study include:

- Chemotherapy
- Cyclosporine, Tacrolimus
- Sirolimus, Everolimus
- Azathioprine
- Cyclophosphamide
- Methotrexate
- Mycophenolate
- Leflunomide
- Biologics/Monoclonals: abatacept, adalimumab, alemtuzumab, anakinra, basilizimab, belimumab, bevacizumab, brodalumab, canakinumab, certolizumab, cetuximab, daclizumab, eculizumab, etanercept, golimumab, infliximab, interferon, ixekizumab, muromonab, natalizumab, omalizumab, rituximab, secukinumab, tocilizumab, trastuzumab, ustekinumab, vedolizumab

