### **8.11.2 Concomitant Medications**

Concomitant medications will be recorded from Day 1 through Day 10, or until discharge, whichever comes first. The name, dose and frequency of all medications that the patients are taking will be recorded, including vasopressor(s) and highest dose of vasopressors. Pain medications and anti-pyretic medications, the time of administration of the individual doses, and the route of administration will also be recorded. Generic names should be used when possible.

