#### **8.11.12 Numeric Pain Rating Scale (PNRS)**

In patients who are able to self-report their pain, the Pain Numeric Rating Scale ([Appendix 8](#)) will be used to grade the severity of the abdominal pain from Day 1 – 10, or until discharge if occurring earlier. The timing of the last dose of an analgesic prior to assessing the patient's pain

should also be recorded. The characteristic of the pain and the similarity to the presenting pain will also be recorded.

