6.2 Prior and Concomitant Medications

Prior and concomitant medication data will be listed and tabulated by ATC code. Prior and concomitant medications will be coded according to the World Health Organization (WHO Drug Dictionary) classification system.

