7.3 Secondary Endpoints - PASS score

7.3.1 Definition

The definition of the PASS score is in accordance with the description below:

Calculated every 12 hours from 1st vital signs taken in the Emergency Department

Organ Failure Score: # Organs x 100 for each system

Organ Failure Definition: Modified Marshall Scoring System (adapted from Banks et al⁴)

Organ system	Score				
	0	1	2	3	4
Respiratory (PaO ₂ /FiO ₂)	>400	301–400	201–300	101–200	≤101
Renal					
Serum creatinine, µmol/L	≤134	134–169	170–310	311–439	>439
Serum creatinine, mg/dL	<1.4	1.4–1.8	1.9–3.6	3.6–4.9	>4.9
Cardiovascular (systolic blood pressure, mmHg) ^b	>90	<90, fluid responsive	<90, not fluid responsive	<90, pH <7.3	<90, pH <7.2

^aA score of 2 or more in any system defines the presence of organ failure

^bOff inotropic support

- Mechanical ventilation counts as respiratory organ failure
- New onset dialysis included as renal failure

SIRS (Systemic Inflammatory Response Syndrome): # SIRS Criteria satisfied x 25 for each criteria. (See below)

- Heart Rate > 90 beats per minute
- Temperature > 38 Celsius or < 36 Celsius
- White blood cell count < 4000 or > 12000
- Respiration > 20/minute

Take the most extreme value within each 12 hour window

Take the WBC from the most recent prior CBC if none available in a given 12 hour window

Abdominal Pain Score: Abdominal pain (0-10) x 5

- Highest numerical value in each 12 hour window

Morphine Equivalent Dose Score: Morphine Equivalent Dose x 5

- For consistency will be using IV MED (typical MED is for oral)
- Common conversions: (easiest to convert to IV)
- Morphine IV to PO is 1 to 3 (ie morphine 10 mg IV = 30 mg PO)
- Dilaudid IV to PO is 1 to 4 (ie dilaudid 1.5 mg IV = 7.5 mg PO)
- Dilaudid IV to Morphine IV is 1:7
- Note: 1 po MED = 30 mg oral morphine
- (refer to tables for more specific conversion)

	Parenteral	Oral
Morphine	10	30
Buprenorphine	0.3	0.4 (sl)
Codeine	100	200
Fentanyl	0.1	NA
Hydrocodone	NA	30
Hydromorphone	1.5	7.5
Meperidine	100	300
Oxycodone	10	20
Oxymorphone	1	10
Tramadol	100	120

Equianalgesic dose conversions. For calculation of Pancreatitis Activity Score:

1 MED (morphine equivalent dose) = 1 mg parenteral morphine = 3 mg oral morphine.

Tolerating Solid Diet Score: (yes=0, no=1) x 40

- Retrospective analysis: based on change in diet order
- Prospective analysis: tolerating at least 50% of solid meal without increase abdominal pain or vomiting

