7.12.3 Presentation

The CPOT will be presented using summary statistics with graphs over time presenting the mean, absolute and percent change.

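### PNRS and CPOT are to be presented without opioid dose beside them, so the planned summary tables cannot separate the pain curves from opioid use

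*SAP*

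**What the plan says.** **Pain endpoints.** PNRS asks for pain at the moment of asking (SAP 7.11.1). Protocol 8.2 to 8.8 schedules it, with CPOT, once per study day through Day 10. On output, SAP 7.11.3 states: "The PNRS will be presented using summary statistics with graphs over time presenting the mean, absolute and percent change". SAP 7.12.3 states: "The CPOT will be presented using summary statistics with graphs over time presenting the mean, absolute and percent change". For PNRS, section 7.11.2 adds: "No statistical tests will be performed", and 7.12.2 says the same for CPOT.

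**Analgesia.** Protocol 1.1 describes opioids as the usual initial analgesic. Protocol 5.3 states: "Any medication, with the exception of those listed below, may be given at the discretion of the PI". Its list covers immunosuppressive and related agents and contains no opioid. Treatment is open-label (Protocol 3.1).

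**Data collected.** Protocol 8.11.2 records name, dose and frequency of all medications, and adds: "Pain medications and anti-pyretic medications, the time of administration of the individual doses, and the route of administration will also be recorded". Protocol 8.11.12 also asks for "The timing of the last dose of an analgesic prior to assessing the patient's pain", and 8.11.13 asks for the same with CPOT.

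**Where opioid use appears in the SAP.** There are two places. Section 6.2: "Prior and concomitant medication data will be listed and tabulated by ATC code". Section 7.3.1, within PASS: "Morphine Equivalent Dose Score: Morphine Equivalent Dose x 5".

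**The concern.** When analgesia is titrated freely by staff who know the allocation, a pain score measures the pain left after treatment. A lower curve in one arm may reflect the study drug, more opioid, or both. Two overlapping curves may mean no effect, or equal comfort reached with less opioid in one arm. A pain score needs the analgesic dose beside it before any of these can be told apart.

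The protocol collects what is needed, but SAP 7.11 and 7.12 use neither the doses nor the last-dose times. At stake is the interpretation of two listed secondary efficacy endpoints in a study that Protocol 1.6 says will support a dose-response reading of efficacy. No tests or adjusted analyses are planned for these endpoints, so the displayed curves are the whole result.

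**Working it through.** **1. Group sizes.** Cohorts of 4, 4, 8 and 8 (Protocol 3.1) sum to 24, the stated sample size. Allocation at 3:1 gives:
- CM4620-IE: 3 + 3 + 6 + 6 = 18, of which 6 are on the first-phase regimen and 12 on the second-phase regimen
- Supportive care: 1 + 1 + 2 + 2 = 6

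The standard error of a difference in means, in SD units, is √(1/18 + 1/6) = 0.47. A chance imbalance in opioid use of about half an SD between arms is therefore unremarkable. In a group of 6, one patient whose PNRS reads 1 instead of 7 moves the group mean by 6/6 = 1 point.

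**2. Exchange rate implied by the SAP.** PASS weights abdominal pain (0 to 10) by 5 and morphine-equivalent dose by 5. With the unit taken as 1 mg parenteral morphine, one pain point equals 1 mg.

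**3. Illustration.** The pain and dose values below are assumptions, taken per 12-hour PASS window. They show that a conflict is possible, not that it will occur.

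| Case | Pain | IV morphine equivalent | 5 × pain + 5 × mg |
|---|---|---|---|
| Arm X | 4 | 10 mg | 20 + 50 = 70 |
| Arm Y | 6 | 4 mg | 30 + 20 = 50 |
| Arm Y, alternative | 4 | 4 mg | 20 + 20 = 40 |

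X against Y: the pain curve favours X by 2 points, while the two PASS items together favour Y by 20. X against the alternative Y: the pain curves coincide, while Y uses 6 mg less, worth 30 PASS points.

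**4. Can the reader recover this from PASS?** The total also adds 100 per failing organ, 25 per SIRS criterion and 40 for not tolerating solid diet. The 20-point difference is smaller than one SIRS criterion and half the diet item. SAP 7.3.1 and 7.3.3 name only the score and its changes for output. By contrast, 7.8.3 asks for items as well as totals for SOFA, and 7.2.3 asks for each scale for CTSI.

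**5. Can the reader recover it from the medication table?** An ATC table shows which drugs were used. Raw milligrams cannot be summed across opioids: the SAP's own conversion table equates 10 mg parenteral morphine with 1.5 mg hydromorphone and 0.1 mg fentanyl. A by-arm dose summary needs a conversion that 6.2 does not call for.

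**6. Is the conversion ready to use?** No. SAP 7.3.1 contradicts itself:
- One note sets one oral MED at 30 mg oral morphine. A later line sets one MED at 1 mg parenteral or 3 mg oral morphine. For 30 mg oral morphine the first gives 1 MED (5 PASS points) and the second gives 30/3 = 10 MED (50 points), a tenfold gap.
- Hydromorphone IV to oral is given as 1 to 4, but its own example, 1.5 mg to 7.5 mg, is 7.5/1.5 = 5, so 1 to 5. An oral dose of 7.5 mg becomes 7.5/4 = 1.875 mg IV under one and 1.5 mg under the other, a ratio of 1.25.

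**The case against.** The SAP does not ignore opioids. PASS is a listed secondary endpoint, counts morphine-equivalent dose, and is to be tabulated and graphed. In both illustrated comparisons it would register the difference, other items being equal. SAP 4.5 promises that all collected data will be summarised and listed, and 6.2 lists concomitant medications. With 24 patients, a reader could compare pain with opioid use patient by patient. Pain as observed under usual care is also a legitimate description, the primary endpoints are safety, and the study is not powered for inference.

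Most of this stands. A reader might infer that the plan takes no account of opioid dose at all. PASS and the listings show otherwise. A reader might also infer that the arm given more opioid will be shown as having less pain. The documents give no opioid doses by arm and no direction, and the bias can equally run the other way.

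What does not stand is that these outputs fill the gap. The PASS total pools opioid with unrelated items, and the general sentence in 4.5 names no converted dose by arm and day. Listings allow case-by-case reading but do not accompany the mean curves from which the arms will be compared.

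**Conclusion.** The point holds in a limited form. PNRS and CPOT are to be shown without opioid dose alongside, and the only dose-based measure is pooled inside the PASS total. In the planned summary tables, neither a difference nor a similarity in the pain curves can be read apart from opioid use.

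The size of any distortion cannot be computed from the documents. The illustrated differences of 20 and 30 PASS points rest on assumed values and on the 1 mg parenteral reading of the MED unit. The conclusion itself rests only on open-label discretionary analgesia, opioids as usual care, and the absence of a named by-arm dose summary. The consequence is confined to interpreting secondary, descriptive pain results. It does not touch the primary safety endpoints. It is worth correcting because the correction is inexpensive and changes what the pain curves can support.

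**What to change.** 1. Reconcile the two MED definitions and the two hydromorphone ratios in SAP 7.3.1 first, since PASS already depends on them. Which conversion to use is for the sponsor to settle and document.
2. In SAP 7.11.3 and 7.12.3, add a table and plot of daily IV morphine-equivalent dose by treatment, dose group and day, placed directly beside PNRS and CPOT.
3. In SAP 7.3.3, present the PASS pain and opioid components separately from the total.
4. In the listings, show the recorded last-analgesic time next to each PNRS and CPOT reading.

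Two tempting additions are better left out. A daily sum of 5 × PNRS and 5 × mg should not become the basis for statements about pain. PASS is computed every 12 hours from the highest pain in the window, so pairing a full day's opioid with one pain reading roughly doubles the opioid weight at a steady dose. Splitting the scores by analgesic use within a fixed number of hours, such as 4, conditions on a post-randomization variable in groups of about 6, 6 and 12, and the documents give no basis for a cut-off.

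The cost is SAP wording, a few extra outputs and the work of settling the conversion. No new assessment is needed and patient care does not change. It should be done before database lock.
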